Visit 2: This visit will take approximately 1 hour to complete. During this visit, participants will be randomized to one of three study conditions. All participants will complete additional study measures. Two-thirds of all participants will receive a smartphone. Those who are randomized to the smartphone groups will be shown how to use the phone to complete assessments, and how to use the app features. Researchers will utilize the participant's Google Play Store account to download the Insight app. Those participants who are randomized to receive smart phones during visit 2 will have an app blocker installed on their phone to prevent phone loss. This app blocker will prevent the participant from access to the phone settings, the Google Play Store or allow deletion the Insight App. Only the research staff will have the password required to access those functions or delete the Insight App. At visits 3 or visit 4, the app blocker will be removed for participants who completed 50% or more of the daily EMA Surveys over the past 30 days as an additional incentive. At the conclusion of the study, the Insight app, and all app data will be removed from the phone, and the phone will be given to the participant to keep. The study data will be removed from the phone and all data collection through the Insight application will end. Researchers will delete the app from the phone and advise the participant the study has concluded. At visit 2, study participants will receive three referral coupons to pass on to others who are interested in the study. If a coupon recipient successfully completes visit 1, the participant who made the referral will be compensated \$20 on the study credit card, for a maximum of 6 successful referrals. Each coupon will include a random unique identification number that identifies the person who provided the coupon and will be valid for the 6 months the participant is active in the study. Participants will be given up to 6 coupons in total if the initial coupons have been distributed. The study team may replace lost or destroyed coupons at their discretion. Participants have a 14-day period to complete visit 2 and be randomized into one of the study conditions. Participants who are not randomized within the 14-day period will be terminated from the study.

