Aim 3. The detectable effects for analyses based on a complete EMA sample size of 201 participants (allowing for 30% study drop-out; see [name] and Rosenheck³ for follow-up rates in a sample of homeless adults with both serious mental illness and substance abuse), 2-sided tests, alpha=.05, and power=.80 are presented in Table 8. Where appropriate, these estimates account for the fact that repeated observations from the same person will be correlated. The most conservative detectable effects for the GLMM EMA analyses will be presented. Thus, calculations are based on an N of 201 individuals completing 80% of 183 assessments during the 6-month EMA study period for a total of 29,426 EMAs across all participants. Since few EMA studies have been conducted in this population, we computed detectable effects using a reasonable range of intraclass correlation coefficient (ICC) values. Detectable effects estimates depend on the variance inflation factor (VIF)¹³⁴ which is based on both the size of the ICC and the average number of observations per person. The VIFs used to calculate the effective sample size are displayed in Table 8. Thus, using the EMA data, we will be able to detect factors that predict reductions in homeless nights by as little as 3.1 percentage points.

Analyses. Logistic Regression of traditional in-person assessments (e.g., substance use, social support, psychological functioning, quality of life; see Table 7 for other key constructs) and summarized EMA data (e.g., affect, stress, discrimination, alcohol and drug use) will be conducted to identify significant demographic, psychosocial, environmental, and behavioral predictors of re-arrest in the 12 months following the randomization visit (binary outcome). Covariates may include treatment group, age, gender, race/ethnicity, education, type of crime, and other variables as appropriate. Change scores (e.g., change in social support from baseline to the 1-month follow-up visit) will also be examined as potential predictors of re-arrest.

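### Aim 3 makes no provision for correlation within coupon referral chains, so its standard errors may be too small if coupons supply much of the sample

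*Combined protocol and SAP*

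**What the plan says.** **Recruitment (Study Procedures, Visit 2).** At the randomization visit "study participants will receive three referral coupons to pass on to others who are interested in the study"; the total can rise to six. When a recipient completes visit 1, "the participant who made the referral will be compensated" $20, "for a maximum of 6 successful referrals". Recruits who reach visit 2 receive coupons themselves, so chains of several links can form. The link is kept: "Each coupon will include a random unique identification number that identifies the person who provided the coupon".

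**Analysis (Statistics, Aim 3).** Logistic regression is to identify "predictors of re-arrest in the 12 months following the randomization visit (binary outcome"). On adjustment, the plan says: "Covariates may include treatment group, age, gender, race/ethnicity, education, type of crime, and other variables as appropriate". Homeless nights are analysed by GLMM, and the stated task there is to choose a correlation structure for the repeated measures. On detectable effects the plan says: "Where appropriate, these estimates account for the fact that repeated observations from the same person will be correlated". The variance inflation factor is built from the ICC and the average number of observations per person.

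Neither the Aim 3 text nor any other section names a referral chain, a cluster-robust variance, a referral-level random effect or a sensitivity analysis for coupon recruitment. The remark that GLMMs can handle random effects and nesting describes the method in general. The Westfall and Young adjustment deals with multiplicity, not with dependence between people.

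**The concern.** People linked by a coupon are likely to know each other. They may share sleeping places, substance use, exposure to discrimination and contact with police. These are among the predictors and outcomes of Aim 3. If a predictor and an outcome are both alike within a chain, a model that treats people as unrelated overstates the information in the data and its standard errors are too small.

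For the arm comparisons in Aims 1 and 2, individual randomization protects the type I error, because allocation is independent of chain membership. Aim 3 has no such protection: its predictors are observed, not assigned. What is at stake is whether some predictors of re-arrest or homeless nights are reported with more certainty than the data support, in an aim whose results are meant to inform later interventions.

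**Working it through.** **1. The plan's own allowance for correlation.** Two phone arms of 144 with 30% dropout give 2 × 144 × 0.70 = 201.6, which matches the stated 201. Then 201 × 0.80 × 183 = 29,426.4, which matches the stated 29,426 assessments. The inflation factor is 1 + (m − 1) × ICC, with m = 0.80 × 183 = 146.4 observations per person. It works within the person and has no term for chains. The 3.1-point detectable effect cannot be checked, because the values in Table 8 are not in the text.

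**2. Design effect for equal-sized chains.** For chains of k people, outcome correlation ρy and predictor correlation ρx:

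- DE = 1 + (k − 1) × ρy × ρx
- true SE ÷ model SE = √DE
- actual alpha of a nominal 5% test = 2 × [1 − Φ(1.96 ÷ √DE)]

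The documents fix only that one referrer plus six recruits makes 7. The correlations are assumptions.

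| k | ρy | ρx | DE | √DE | actual alpha |
|---|---|---|---|---|---|
| 2 | 0.10 | 0.2 | 1.02 | 1.01 | 0.052 |
| 7 | 0.10 | 0.2 | 1.12 | 1.06 | 0.064 |
| 7 | 0.05 | 1 (fully shared) | 1.30 | 1.14 | 0.086 |
| 7 | 0.10 | 1 (fully shared) | 1.60 | 1.26 | 0.121 |
| any | any | 0 | 1.00 | 1.00 | 0.050 |

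**3. Simulation with unequal, multi-link chains.** 462 people, at most six recruits each, recruiter drawn from the previous 80 enrollees, a logistic model for a binary outcome, and a predictor with no true effect; 2,000 trials per setting. Assumed pairs (predictor correlation, latent outcome correlation): (0.2, 0.1), (0.3, 0.2), (0.4, 0.3). All members of a chain are *equally* correlated.

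| Share referred | Size-weighted mean chain | Ordinary SE | Chain-clustered SE |
|---|---|---|---|
| 30% | 2.1 | .048, .052, .062 | .043, .049, .054 |
| 50% | 4.5 | .044, .059, .081 | .043, .050, .052 |
| 70% | 15.8 | .068, .106, .140 | .067, .070, .075 |

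Monte Carlo error near 5% is √(0.05 × 0.95 ÷ 2,000) = 0.005, so values from about 4% to 6% cannot be told from 5%. A repeat with separately written code and a 50% event rate gave 5.3–6.0%, 4.7–7.6% and 6.8–15.2% with ordinary SEs, and 5.0–5.5%, 4.1–5.2% and 6.7–7.9% with clustered SEs. In round figures, ordinary SEs give about 4–6%, 4–8% and 6–15%.

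**4. Same set-up, correlation decaying along the chain.** Here the assumed correlation applies to a direct coupon pair and falls with each further link (1,500 trials per setting). Ordinary SEs reject 4.9–5.3% at 30% referred, 3.9–6.3% at 50% and 4.9–7.7% at 70%. At the worst setting clustered SEs also reject 7.7%.

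**5. EMA predictors.** These exist only in the phone arms. Thinning 462 people to 201 shortens the size-weighted mean chain from about 15 to 7 at 70% referred, and from 4.4 to 2.5 at 50%. Even with equal correlation, ordinary SEs then reject 4.5–6.5% at 30–50% referred and at most 9.3% at 70%.

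No rejection rate was simulated for the homeless-nights GLMMs. The same mechanism applies to their between-person effects. Within-person, day-to-day EMA effects are less exposed.

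**The case against.** The strongest case against is that the visible inflation needs two things the documents do not show.

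- **A high coupon share.** Participant Recruitment describes jail fliers and Bridge intake as the route in. Recruits must still have been released from jail in the past 60 days and enroll in the Bridge program. Participants start with three coupons, not six. Payment follows visit 1, so a paid referral need not become a randomized participant. Nothing supports a figure as high as 70%.
- **Equal correlation across the whole chain.** Acquaintance is a reason for correlation between direct contacts. It is a weak reason for equal correlation among some 15 people several links apart. With decay, the effect is small and clustering changes almost nothing.

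The plan also does not assert that participants are independent. Its covariate list is open-ended, and the sentence on same-person correlation concerns detectable effects, not the fitted models.

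Most of this stands, and it limits the size of the point. It does not remove the gap: open wording commits to nothing on chains, the logistic model has no stated cluster provision, and the data that would settle the matter are already collected.

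A reader might also infer spillover between arms along coupon links, since under equal allocation a linked pair falls in different arms two times in three. The documents do not support that inference. No section suggests that phones or contacts pass along coupon links, and all participants enroll through the same shelter and can meet without a coupon.

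**Conclusion.** The gap is real and its consequence is conditional. Standard errors for the re-arrest predictors, and for between-person effects on homeless nights, *may* be too small if coupons supply a large share of the sample and both predictor and outcome are alike across whole chains. Under the assumed correlations the actual error of a nominal 5% re-arrest test is about 4–6% at 30% referred, 4–8% at 50% and 6–15% at 70% with equal correlation, and about 4–8% in all settings with decay.

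It is tempting to conclude that Aim 3 predictors *will* be declared significant too often. The documents do not support that: they give no coupon share, chain length or correlation, and under many plausible values the error stays close to 5%. Nor does the point reach the type I error of the randomized comparisons in Aims 1 and 2. This is a low-priority improvement, worth making because it is nearly free.

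**What to change.** Before results are seen, add to the Aim 3 analysis text:

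- a referral-chain identifier derived from the coupon numbers, with each person who came without a coupon and referred no one forming a chain of one;
- chain-clustered robust standard errors in the logistic model for re-arrest;
- a chain random effect, or chain-clustered standard errors, for between-person effects in the homeless-nights GLMMs;
- a report of the share referred and the distribution of chain sizes, so that readers can see whether the matter counts.

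The cost is one derived variable, a cluster option in the models and slightly wider intervals where chains matter. Clustered standard errors do not fully restore 5% when a few chains are very long (about 7–8% in the 70% setting), so very long chains should be noted as a limitation.

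No spillover check is needed for this point. If the sponsor wants one, it should stay within coupon-linked UCM and UCM+SP participants and compare them by the linked partner's randomized arm. Comparing linked with unlinked people would not be a randomized contrast and could give a false signal.

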(e.g., assessing the number of drinks consumed or level of depression or anxiety over the past week or month).^{42,43} Ecological momentary assessment (EMA), in which handheld devices are used to capture “real time” experiences that vary daily (or from moment to moment), is currently the most accurate way to measure phenomena in real time in natural settings.^{42,44} Although EMA has been used in a variety of populations and with multiple health outcomes, only one study⁴⁵ outside of our own work⁴⁶ has collected EMA data in homeless adults. The proposed study will identify key variables, measured proximally (EMA data) and distally (traditional in-person assessments and EMAs), that predict re-arrest and homelessness. These rich data will address knowledge gaps that have limited our understanding of and ability to intervene in this marginalized population.

Overall, the significance of this trial will be to evaluate a technology-driven application to increase access to service providers in a highly vulnerable group of homeless adults and to thereby decrease the likelihood of re-arrest and homelessness. In addition, we hope to improve our understanding of the proximal and distal factors that contribute to homelessness and incarceration recidivism. This contribution is significant because it is a step towards the development of practical, inexpensive, and effective interventions for homeless adults.

Objectives:

Our long-term goal is to reduce health disparities among recently incarcerated homeless adults.

The primary study objectives will be attained by pursuing the following specific aims:

- a. **To compare case management and crisis management service utilization among recently incarcerated homeless adults who are randomized to the UCM, UCM+SP, and SPCM conditions.** It is hypothesized that homeless adults assigned to SPCM will utilize more case management and crisis management services than those assigned to UCM or UCM+SP.
- b. **To compare the effect of treatment condition on alcohol use, drug use, and psychological distress.** It is hypothesized that the SPCM group will demonstrate greater improvements in each outcome compared to UCM+SP or UCM

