1. **Usual Case Management (UCM) group.** The UCM group will receive the standard Homeless Recovery Program currently offered at The Bridge. In order to qualify for the standard homeless recovery program, individuals must complete The Bridge intake and substantiate homelessness (e.g., provide evidence that they spent the previous night in a shelter or jail). The Bridge intake includes a comprehensive needs assessment, and demographic information is obtained. Following intake, Bridge guests receive a day pass that grants them access to many of the services available at The Bridge (e.g., meals, showers, laundry, phone, mail, library, barber shop, and storage space for their belongings). Those who enroll in The Bridge Homeless Recovery Program receive an identification card and can gain access to additional services including case management, Metro Care (onsite mental health and substance abuse counseling), housing assistance, disability/veteran's benefits assistance, job readiness training, legal aid, and bus passes. Although these services are freely available to all guests enrolled in The Bridge Homeless Recovery Program, many services are offered only during normal business hours and in-person visits are the norm.

Bridge case managers are licensed professional counselors and/or Master's level clinicians who adhere to the **Standard Case Management Model**.^{19,47} Case managers assist homeless adults with: 1) developing care and housing plans; 2) making and maintaining linkages to on- and off-site service providers (e.g., mental health and substance abuse providers); 3) obtaining vital documents needed for housing and income (e.g., birth certificates, state identification, social security cards); 4) job readiness training and placement (if appropriate); 5) overcoming barriers related to criminal history; 6) development of and re-connection with support systems; and 7) transitioning from homelessness to appropriate housing. Case managers also advocate on behalf of homeless adults by serving as a connection between all agencies that will be assisting the guest, their families, and any other involved parties. Guests are encouraged to meet with their case managers weekly; however, Bridge data have indicated that those who enroll in the **Bridge Homeless Recovery Program** complete a total of 1.95 and 3.12 case management sessions in the first 1 and 6 months of enrollment, respectively.

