Recent research has indicated that phone prompts can increase service utilization.^{49,50} For example, Lucht showed that twice weekly phone prompts increased phone-based counseling sessions in alcohol dependent patients.⁴⁹ To increase the likelihood that SPCM group participants will use the resources available through the app, the phone will be programmed to automatically prompt/suggest a connection with their Bridge case manager twice per week.

Table 1. SPCM group smartphone application features

Figure 1: SPCM home screen		Feature/Button	Description of feature
	Call My Care Manager	Clicking this button will automatically call the participant's assigned Bridge case manager. Individual Bridge case managers are assigned to all Bridge Homeless Recovery Program enrollees and they are available from 8:00am to 5:00pm Monday through Friday (see letter of support from Bridge CEO).	
	Call ADAPT Crisis Line	Clicking this button will call the free ADAPT mobile crisis line. The crisis line is available 24 hours a day, 7 days a week to help homeless individuals address and overcome crises.	
	Helpful Websites	Clicking this option will lead to a menu of websites that may be useful to participants (e.g., Dallas public transit routes, online support groups (e.g., Narcotics and Alcoholics Anonymous))	
	Call Study Staff	Clicking this option will connect participants to study staff if they encounter problems with the study phone and/or rescheduling missed follow-up appointments.	
	Payment	This button indicates the amount in gift cards that participants have earned for completing EMAs to date. These gift cards will be awarded when each participant presents at The Bridge to complete 1-, 6-month follow-up assessments (see EMA Compensation in section 3.8.b.).	

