All randomized participants will be included in the analyses and the trial will end once 462 participants are randomized and complete all study components. Preliminary data analyses, manuscript preparation, and conference presentations will begin in Year 2.

Aim 1. The number of participants ($n = 144$ in each group) was estimated based on the following assumptions: 1) random allocation of participants between 3 conditions; 2) type I error rate set to 0.05; 3) a 30% dropout rate for each condition;²³ 4) targeted minimum power of 0.9, and 5) a conservative increase of 4.5 case management sessions between the UCM and SPCM conditions across the 6-month study period. The estimated increase in in case management sessions is based on Lucht et al.,⁴⁹ which showed that 20% of all phone-based prompts to connect with an alcohol treatment counselor resulted in actual treatment sessions. Mondays, the daily EMA items and additional items will be assessed. Additional Monday items will cover topics/variables that have less day-to-day variability (e.g., arrest; witnessing crimes or violence; emergency room visits; hospitalization; quality of life). Examples of EMA constructs that will be assessed are listed in Table 3 and actual EMA items are included in the Appendix.

	Compensation (Usual Care)	Compensation (Smartphone Groups)
Visit 1 (Today)		
Questionnaire	\$30	\$30
Visit 2 (Within 3 Days)	\$30	\$30
Visit 3 (1-Month Follow-Up)		
Questionnaire	\$50	\$50
Phone Assessments	N/A	Up to \$50 every 15 days for survey completion (\$100)
Visit 4 (3-Month Follow-Up)		
Questionnaire	\$50	\$50
Phone Assessments	N/A	Up to \$50 every 15 days for survey completion (\$200).
Visit 5 (6-Month Follow-Up)		
Questionnaire	\$50	\$50
Phone Assessments	N/A	Up to \$50 every 15 days for survey completion (\$300).
TOTAL:	Up to \$210	Up to \$810

Analyses. Primary analyses for this aim will compare counts of the total number of case and crisis management sessions that occurred between the randomization visit and the 6-month follow-up across the 3 conditions using analysis of covariance (ANCOVA). Covariates may include race/ethnicity, age, sex, lifetime months homeless, type of arrest (e.g., violent vs. non-violent), substance abuse or mental health diagnoses,

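### Aim 1 is sized on case management sessions alone but tests the sum of case and crisis sessions, so the stated 90% power does not describe the tested count and the total cannot show which service rose

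*Combined protocol and SAP*

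**What the plan says.** The hypothesis under Objectives, aim a, is that SPCM participants "will utilize more case management and crisis management services than those assigned to UCM or UCM+SP". It names two services.

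The sample size under Statistics, Aim 1, names one. The effect is "a conservative increase of 4.5 case management sessions between the UCM and SPCM conditions across the 6-month study period", with "type I error rate set to 0.05" and "targeted minimum power of 0.9", 30% dropout and 144 participants per group. Its support is a study in which "20% of all phone-based prompts to connect with an alcohol treatment counselor resulted in actual treatment sessions". The app's prompts work on the same service: under Study Conditions the SPCM phone will "automatically prompt/suggest a connection with their Bridge case manager twice per week". The crisis line is reached by a separate button (Table 1), and no prompt for it is described.

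The analysis paragraph of Aim 1 then reads: "Primary analyses for this aim will compare counts of the total number of case and crisis management sessions". The period runs from the randomization visit to month 6, the method is ANCOVA, and pairwise comparisons use Tukey-Kramer. No analysis by service is specified.

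The only background rate given is for case management: Bridge enrollees "complete a total of 1.95 and 3.12 case management sessions in the first 1 and 6 months of enrollment, respectively". The documents give no crisis-session rate, no expected crisis effect, and no SD for case sessions, crisis sessions or their sum.

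**The concern.** A power statement holds for one variable with one effect and one SD. Here the variable changes between the sample-size paragraph and the analysis paragraph. Crisis sessions add their own variance to the tested count, and they add to or subtract from the 4.5-session difference by an amount the plan does not state. The reasoning behind 4.5, prompts that turn into sessions, does not extend to a service that is not prompted.

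Interpretation is also at stake. A significant total could come from case management alone, crisis contacts alone, or one rising by more than the other falls. A null total could hide a real gain in case management. The plan has no prespecified analysis that would tell these apart.

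**Working it through.** **Inputs from the plan.** Difference 4.5 case sessions; power 0.90; alpha 0.05; 144 per group; 30% dropout. Completers per group: 144 × 0.70 = 100.8, taken as 101.

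**Assumptions.** Two-sided test (sidedness is not stated for Aim 1); normal approximation; 144 is the number enrolled; no precision gain from covariates.

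**The plan's own figure.** The 144 cannot be reproduced, because no SD is given. It can only be solved backwards:

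- SD = 4.5 / [(1.960 + 1.2816) × √(2/101)] = 4.5 / (3.2415 × 0.1407) = 9.87.
- With the Tukey critical value for three groups, 2.355: SD = 4.5 / [(2.355 + 1.2816) × 0.1407] = 8.79.

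These are the SDs at which the plan's statement would be true for case sessions. They are not reported values.

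**Power for the sum.** Let s be the SD of crisis sessions (assumed, uncorrelated with case sessions) and c the effect of SPCM on crisis sessions. Then SD of the total = √(9.87² + s²), and power = Φ[(4.5 + c) / (SD of the total × √(2/101)) − 1.960].

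| Assumed crisis SD | SD of total | c = 0 | c = +1 | c = −1 |
|---|---|---|---|---|
| 3 | 10.31 | 87% | 97% | 67% |
| 5 | 11.06 | 82% | 94% | 61% |
| 10 | 14.05 | 62% | 79% | 42% |

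One cell in full, for s = 5 and c = 0: 11.06 × 0.1407 = 1.556; 4.5 / 1.556 = 2.891; Φ(2.891 − 1.960) = 0.82.

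With the Tukey critical value and SD 8.79, the c = 0 column becomes 86%, 79% and 52%.

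**Attribution.** The formula uses only the sum of the two effects. No case effect with 4.5 extra crisis sessions therefore gives the same 87%, 82% and 62% chance of a significant total as 4.5 extra case sessions with no crisis effect. The test cannot separate the two.

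**Where the 4.5 comes from.** Two prompts a week for 26 weeks is 52 prompts; 20% of 52 is 10.4 sessions, and the plan takes the lower 4.5. Every step concerns contact with the case manager.

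**The case against.** The strongest reply is that the total is a fair measure of what the trial wants. Study Design names service utilization as a primary outcome, the General Information section expects SPCM to raise use of both services so that unmet needs are addressed, and the app has a one-touch crisis button. If crisis use rises as hypothesised, power for the total can exceed 90%, as the c = +1 column shows at SD 3 and 5. This stands: the mismatch does not prove a loss of power.

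The inputs are also soft. The crisis SDs are assumed, and the largest exceeds the back-solved case SD. The case SD is itself inferred. If the 462 participants are split equally, each arm has 154, or 154 × 0.70 = 107.8 completers, and power at crisis SD 3 with no crisis effect is 89%, close to target. This also stands, and it is why the table shows a range and not an estimate.

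The analysis sentence might mean a separate count for each service. That is the less natural reading of a total, and one sentence would settle it.

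Two stronger readings are tempting. A reader might infer that worsening crises would be scored as benefit. The documents do not support that: the outcome counts use of a service, more use is the intended direction, and Aim 2 compares psychological distress separately. A rise in crisis contacts is ambiguous, not an error. A reader might also infer that the Aim 1 hypothesis cannot be answered at all. That goes too far, because the total does answer a question about overall use; it does not answer the question for each service.

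None of this supplies the missing SD and effect for the tested count, or a prespecified analysis by service.

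**Conclusion.** The point holds as a mismatch between the powered count and the tested count. The 90% applies to case management sessions only. For the sum, power could be about 87%, 82% or 62% if crisis use is unaffected, or about 97%, 94% or 79% if SPCM adds one crisis session, at assumed crisis SDs of 3, 5 and 10. These figures rest on the back-solved SD of 9.87, 101 completers per arm, a two-sided 0.05 test and uncorrelated counts. The documents do not say which case applies, so the direction of the power error is unknown.

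The limit on interpretation needs none of these assumptions: an unweighted total cannot show which service increased, and the hypothesis names both. This is worth correcting because the correction is cheap and changes what Aim 1 can conclude. It does not invalidate the trial.

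**What to change.** In the Aim 1 analysis paragraph:

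1. Make the number of case management sessions from the randomization visit to month 6 the primary count, matching the sample-size paragraph.
2. Make crisis contacts a second Aim 1 outcome, tested only after the case count succeeds or under a stated multiplicity adjustment across the two. Use a model suited to counts, such as negative binomial regression.
3. Report the total as supportive.

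If the investigators prefer to keep the total as primary, state that the 90% power applies to case sessions only, and prespecify both component analyses. Giving an SD and an expected effect for the total would be better still, if data exist.

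The cost is SAP wording and one extra model. No new data are needed, because both counts are already required to form the total. The downside is that Aim 1 has two results to report instead of one, and they may differ.

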and education. The Tukey-Kramer adjustment will be used to examine all pairwise comparisons across conditions. We will also determine if the intervention has similar effects across races, gender, and age**Aim 2**. Based on the available data in criminal justice and homeless populations, we expect a 30% reduction in alcohol and drug use days in SPCM and a 15% reduction in alcohol and drug use days in UCM+SP compared with UCM.^{3,126} Given these expected differences, the proposed sample size of 462 participants (144 per condition) will yield 90% minimum power for comparing the frequency of alcohol and drug use days across conditions. Furthermore, the proposed sample size of 462 participants has 80% minimum power to detect a 24% greater decrease in psychiatric symptoms¹²⁷ in the SPCM group and 10% greater decrease in the UCM+SP group relative to UCM.

Analyses. Multi-level models, also known as mixed models will assess the impact of condition on alcohol and drug use and psychological distress. This method considers the auto correlated nature of this data, and 'unstructured' covariance may be specified to account for the unequal spacing of observations (in-person and EMA data). Covariates for analyses will include baseline characteristics that are known predictors of each outcome, including age, race/ethnicity, employment status, criminal history, and periods of lifetime homelessness. We will also test for interactions between treatment and key demographic variables (e.g., race, ethnicity, gender, and age).

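### Aim 1's listed sizing assumptions name one contrast at alpha 0.05, but the planned test is Tukey-Kramer over three pairs; if the sizing was unadjusted, power for SPCM vs UCM is about 82% to 84%, not 90%

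*Combined protocol and SAP*

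**What the plan says.** In the Statistics section, Aim 1, the listed sizing assumptions include "type I error rate set to 0.05", "targeted minimum power of 0.9", 30% dropout in each condition, and "a conservative increase of 4.5 case management sessions between the UCM and SPCM conditions across the 6-month study period". The result is 144 per group. The list gives no SD, no sidedness and no adjustment for several comparisons.

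The analysis paragraph for the same aim plans an ANCOVA on the session count and then says: "The Tukey-Kramer adjustment will be used to examine all pairwise comparisons across conditions". No order or priority among the three pairs is given.

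Under Objectives, aim a, the hypothesis is that SPCM participants "will utilize more case management and crisis management services than those assigned to UCM or UCM+SP". Two of the three pairs therefore carry the hypothesis. An effect size is stated for only one of them, SPCM vs UCM.

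**The concern.** A sample size found for one comparison at 0.05 does not give the same power when that comparison must pass the Tukey-Kramer threshold for three pairs. The adjustment is equivalent to testing each pair at about 0.019. On the natural reading of the sizing list, the stated 90% then belongs to a test that will not be run.

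Service utilization is one of the primary outcomes named under Study Design. The chance of missing a true 4.5-session effect would rise from 10% to about 18%. With only three groups, part or all of that loss on SPCM vs UCM can be avoided without more participants and without giving up familywise control.

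**Working it through.** **Inputs from the plan.** Difference 4.5 sessions (SPCM vs UCM); alpha 0.05; power 0.90; dropout 30%; 144 per group; total 462; Tukey-Kramer over three pairs.

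**Not in the plan.** The SD of the session count (only a usual-care mean is given: enrollees "complete a total of 1.95 and 3.12 case management sessions in the first 1 and 6 months of enrollment"), the sidedness for Aim 1, whether 0.05 is per comparison or familywise, and any effect for SPCM vs UCM+SP. Two-sided testing is stated only for Aim 3 ("2-sided tests, alpha=.05, and power=.80") and is assumed here.

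**Step 1. The plan's own figure.** The usual formula is n per arm = 2 × SD² × (z for alpha + z for power)² / 4.5². Without an SD, 144 cannot be reproduced; it can only be inverted. Completers per arm are 144 × 0.7 = 100.8. That 144 is the number before dropout is supported by Aim 3, where 2 × 144 × 0.7 = 201.6 matches the 201 given. The implied SD is 4.5 / (noncentrality × √(2/100.8)):

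- unadjusted two-sided 0.05: noncentrality 1.960 + 1.2816 = 3.2415, SD 9.86
- one-sided 0.05: noncentrality 2.9264, SD 10.92
- Tukey already built in: noncentrality 2.3437 + 1.2816 = 3.6253, SD 8.81

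Nothing in the plan chooses among these.

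**Step 2. Power under Tukey-Kramer if the sizing was unadjusted and two-sided.** The SD is not needed, because 90% power at 0.05 fixes the noncentrality at 3.2415. The Tukey critical value for three groups is q(0.95; 3, ∞)/√2 = 2.3437, so power = Φ(3.2415 − 2.3437) = Φ(0.898) = 81.5%. With noncentral t (101 completers per arm, critical value 2.355 on 300 error df) it is 81.6%.

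**Step 3. The other sample size in the plan.** 3 × 144 = 432, but the target is 462, or 154 per arm. With the same SD and 30% dropout, noncentrality is 3.2415 × √(154/144) = 3.352, and power = Φ(3.352 − 2.344) = 84.3%. The unadjusted test would have 91.8%.

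**Step 4. Other sizing bases at 144 per arm.** Tukey-Kramer power for SPCM vs UCM:

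| Basis of the 90% | Power |
|---|---|
| Two-sided 0.05, one comparison | 81.5% |
| One-sided 0.05, one comparison | 72.0% |
| Three-group omnibus F | 77% to 89%, depending on the UCM+SP mean |
| Already sized for Tukey | 90.0% |
| Bonferroni 0.05/3 | 90.9% |

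**Step 5. Alternatives.** Simulation with the noncentrality of Step 2. Step-down Tukey here means: if the largest of the three differences passes the Tukey threshold, each pair is then tested at two-sided 0.05.

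| | Single-step Tukey | Step-down Tukey | Fixed sequence |
|---|---|---|---|
| SPCM vs UCM, UCM+SP equal to UCM | 82% | 87% | 90% |
| SPCM vs UCM, UCM+SP halfway | 82% | 83% | 90% |
| Both SPCM contrasts, UCM+SP equal to UCM | 71% | 82% | 83% |
| Both SPCM contrasts, UCM+SP halfway | 22.5% | 35% | 36% |

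Under the global null, the chance of any rejection is 5% for all three.

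**Step 6. Recovering 90% by recruitment.** The ratio is (3.6253/3.2415)² = 1.251, and 144 × 1.251 = 180.1. That means 181 per arm, or 543 in total.

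**The case against.** The strongest objection is that the sizing may already have allowed for Tukey. No SD or formula is given, an SD of 8.81 would fit 144 per group with no loss, and silence about an adjustment does not prove its absence. This stands. A reader might infer that the trial definitely has 82% power for its main contrast; the plan does not support that as a fact. What remains is that the list presents the assumptions used, a multiplicity allowance would be a material one, and it is not there.

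Second, the statistics section includes all randomized participants in the analyses. If session counts were available for all 154 per arm, Tukey power at the same SD would be about 95%. But the sizing itself counts on 30% loss, and the three data sources listed do not include shelter service records, so complete counts are not assured.

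Third, ANCOVA may gain precision. Covariates explaining 10% or 20% of the variance would lift 82% to about 86% or 90%. Those shares are assumptions, the covariates are only ones that may be included, and the unstated SD could already be a residual SD.

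Fourth, Tukey-Kramer is valid and prespecified, and aim a does compare all three conditions. That is correct. The point is efficiency and agreement with the sizing, not error control.

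**Conclusion.** The sizing list and the planned test do not match on paper. If the 0.05 was two-sided and per comparison, power for SPCM vs UCM is about 82% at 144 per arm, or about 84% at 154 per arm, both less 30% dropout, against a stated minimum of 90%. Whether the loss is real depends on an SD and an alpha basis that the plan does not give.

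Two further inferences are not supported. A reader might conclude that ordering the tests restores power for the whole of hypothesis a. It restores 90% for SPCM vs UCM only. No effect is stated for SPCM vs UCM+SP, and the chance of showing both contrasts falls to about 36% even with a fixed sequence if UCM+SP lies halfway, which is the pattern Aim 2 expects for substance use (15% against 30%). A reader might also extend the point to Aim 3, where detectable effects use 0.05 and Westfall-Young adjustment is planned. That adjustment is resampling-based and has no fixed level at which those effects could be restated.

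**What to change.** Replace single-step Tukey-Kramer in the Aim 1 analysis, before any comparative data are seen, with one of the following:

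- a fixed sequence, each test at two-sided 0.05: SPCM vs UCM, then SPCM vs UCM+SP, then UCM+SP vs UCM. This gives SPCM vs UCM the full power of the unadjusted test.
- a step-down Tukey procedure. It rejects whenever the single-step test does and sometimes more, but does not fully restore 90% for SPCM vs UCM.

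If Tukey-Kramer is kept, state the SD and its source, the sidedness, and whether 0.05 is per comparison or familywise. Then restate power for the test used (about 82% to 84% if the sizing was unadjusted). In either case, reconcile 144 per group with the total of 462, and say what effect, if any, is expected for SPCM vs UCM+SP.

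The cost is wording in the statistics section and no participants. The downside is that simultaneous intervals become descriptive and, under a fixed sequence, a failed first test ends formal testing.
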